2.2 Study Rationale

Preliminary Studies/Progress Report

Over the past 10 years we have executed a line of research focused on pain-related fear avoidance in children spanning assessment and treatment intervention development.

We have implemented the first US pilot of graded in-vivo exposure for youth with chronic pain (**GET Living**; NCT:01974791). GET Living was designed in close consultation with **[name]**, developer of GET and consultant on this application. The pilot was designed as a sequential replicated and randomized single-case experimental design with multiple measures with no comparator arm.

Preliminary Clinical Endpoints without Controls. As displayed in **Table 1**, patients reported significant improvements in disability, fear, avoidance (large effects). Moreover, parent fear, avoidance, and protective behavior were also impacted (large effects). These results suggest that

1) GET Living treatment results in significant improvements in primary (disability) and secondary/mechanistic (fear, avoidance) endpoints, 2) gains continue at 3 and 6-months follow-up, and 3) this approach is particularly effective for parents on fear, avoidance, and protective behavior.

In addition to standard questionnaires, patients complete the **Photographs of Daily Activities-Youth English (PHODA-YE)**⁴⁶, a diagnostic tool we validated to determine perceived harmfulness of activities and movements. The PHODA-YE is administered electronically with a photograph for each activity. Treatment providers receive a detailed PHODA-YE

report that is shared with the patient to develop an exposure hierarchy prior to the start of exposures.

[figure not shown]
Examining PHODA-YE outcomes (**Figure 2**), patients report significant decreases in activity-engagement worries (large effect sizes across domains), with largest sports activity engagement improvements. *These results suggest that specifically targeting worrisome activities in GET Living treatment results in appreciable improvements at end of treatment that are maintained.*

The proposed study focuses on evaluating an innovative treatment adolescents with pain-related disability and fear. GET is successful and empirically supported for reducing disability in adults with substantial pain-related fear. However, the efficacy of exposure-based treatment for children with chronic pain has not been tested.

Feasibility and Acceptability Data. A total of 37 patients (Mean age=13.7; 82% female) enrolled. Of the 34 patients who began treatment (3 dropped out during baseline), 28 completed (18% attrition rate) and 27 have reached 3-months with one lost to follow-up (96% follow-up retention rate). Average duration of treatment for completers was 64 days with an 86% patient daily diary completion rate and 82% for parents. Families also provided feedback at discharge interviews: "My son gained confidence, and I was taught how to support him" (mom), "I can break activities down- it doesn't have

Table 1. GET Living Outcomes

Outcome	Admit	Discharge	3-mos	□2
Adolescent (n=26)				
Pain-related Fear (0-96)	52.2	36.3	30.7	0.36**
Disability (0-60)	24.8	15.8	11.3	0.51**
Pain (0-10)	5.9	4.5	3.7	0.26*
Parent (n=23)^a				
Pain-related Fear (0-52)	37.9	24.5	21.4	0.71**
Protect (0-4)	1.5	1.0	0.8	0.62**

■ Baseline ■ Discharge ■ 3-Month

Figure 2. PHODA-YE Outcomes (n=26)

Note. ^aOne young adult participated without a parent. Two parents did not complete follow up self-reports; **p<0.001; *p=0.001

to be all or nothing" (patient). *Developmentally sensitive modifications*. "The word "worry" was used too often." (mom and dad). Patients also struggled distinguishing between numerical ratings of worry and pain. In response, we developed a rating scale for exposure activities based on **W**: Willingness, **I**: Importance, **L**: Likelihood of Success, and **D**: Degree of Difficulty (**WILD** scale). "Diaries became repetitive" (patient). In response, we created multiple versions of the diaries with items in varying order. Families requested 'coping tools'. In response, we devised exposure action plans (EAP) to increase task persistence (e.g., movement break, music during task).

3. STUDY DESIGN

This study employs a two-group randomized, controlled design to test GET Living, for adolescents with chronic musculoskeletal pain and elevated pain-related fear (**Figure 3**). **Primary outcome** is pain-related fear avoidance (adolescent, parent). **Secondary outcome** is disability. Additional outcomes are parent responses to pain and pain acceptance. Exploratory: adolescent biomechanics and physical activity.

[figure not shown]

Figure 3. Study Design. a) Eligibility Screening: musculoskeletal pain patients (ages 8-18; pain > 3 months) at Stanford Children's Health (SCH); b) Baseline Visit (BAS): Consent/Accent, Baseline Assessment: SR, motion analysis; Baseline Daily Diary: DD and actigraphy; c) Randomization: randomization to treatment group; d) GET Living and TPM begin: DD and actigraphy ongoing; e) Discharge Assessment: SR, motion analysis; f) 3-month Follow-Up: SR, 7-day DD, g) 6-month Follow-Up: SR, 7-day DD. Note. **DD**=daily diary; **SR**=self-report; **W**=week.

Recruitment. An ideal recruitment site, Stanford houses a tertiary care pediatric pain management treating approximately 300 unique patients in the clinic each year. We will recruit adolescent patients and a primary parent ($N = 74$) from the outpatient pediatric pain management clinic (PPMC) at Stanford Children's Health (SCH). We will also recruit patients from Kaiser Permanente Bay Area satellite clinics, contingent upon referrals from pain rehabilitation clinicians. **For inclusion**, the patients: 1) are 8-18 years old; 2) have musculoskeletal or neuropathic pain (e.g., localized [back, limb], diffuse)⁴⁷ not due to an acute trauma (active sprain or fracture); 3) have pain-related fear (FOPQ ≥ 35), 4) functional limitations (FDI ≥ 13), and 5) be English language proficient. **Patient exclusion criteria are:** 1) significant cognitive impairment (e.g., brain injury) and 2) significant medical or psychiatric problem that would interfere with treatment (e.g., seizures, psychosis, suicidality). **Identification of Eligibility:** Patients and their parents who meet eligibility criteria will be informed of the study by their pain clinicians at clinic appointments and provided a study brochure. Additionally, a study flyer will be posted on our bulletin board of all active clinical studies in the patient waiting room. **Screening:** For each patient referred to the trial, eligibility for enrollment will be determined by the GET Living research team via chart review, along with the Clinician Referral Checklist (MOOP Supplemental Materials I) and a screening phone call. **Study Entry and Randomization:** Individuals passing the first two stages will enter the study by attending the Baseline Assessment visit (BAS). Once enrolled, adolescents will be randomized to either GET Living or TPM and stratified on fear (moderate/high; FOPQ-C: low [0-34] moderate [35-49] high [50-96]) and disability (moderate/severe; mild [0-12] moderate [13-29] severe [30-60]⁴⁸), to minimize the possibility of imbalance between the two treatment arms. To allow the use of small blocks while minimizing the probability of a blinded staff member predicting the next assignment, we will use blocks of size two and four and randomly choose block sizes. The study biostatistician (**[name]**) will create separate randomization lists for each of the four strata prior to the start of patient recruitment with each list long enough to include the total planned study size. A series of block sizes (either two or four, with probability weights two thirds and one third respectively) will be randomly created and within each block half will be randomly assigned to GET Living and the other half to TPM. Copies of the randomization lists will be kept by the biostatistician and Research Coordinator and not shared with other members of the team. The

biostatistician will also create a randomization scheme to determine the number of days for the pre-treatment baseline period for each individual participant (2 weeks on average).

Study Procedures. At the BAS visit participants will complete informed assent/consent, complete baseline questionnaires, begin daily diaries, and begin wearing an Actigraph. Child participants will undergo biomechanical assessment (**[name]**, Director of the Motion and Sports Performance Laboratory at SCH) during this visit. Notification of treatment arm allocation will occur at the end of the pre-treatment baseline period, and treatment will begin according to randomized group allocation: GET Living or TPM. Discharge testing occurs at the end of GET Living or TPM and includes participant questionnaires, child biomechanical assessment, and an exit interview. Daily diary and actigraphy ends at discharge. At 3 and 6 months follow-up, participants complete daily diaries for 7-days and self-report questionnaires.

Treatment Conditions. Participants will be randomized into: **GET Living or Typical Pain Management (TPM)**. During the study, participants will be instructed to not seek new treatments for pain. **GET Living.** An outpatient team consisting of a pain psychologist and physical therapist (PT) provide GET Living, both trained in this modality of treatment by [name] with ongoing consultation from [name] (lead innovator of GET in adults) and exposed to treatment session videos from participants in the pilot. GET Living is focused and individually tailored. The primary aim of GET Living is returning to valued activities of daily life and restoring daily functioning, including return to school. The treatment manual, entitled **GET Living: Graded Exposure Treatment for children and adolescents with chronic pain** was adapted from the adult treatment manual⁴⁹ (see **Section 5.1** detailed description). The protocol consists of 12 50-minute sessions delivered twice a week for up to 12 weeks. Sessions 1-5 (education, formulation, goals) are conducted with the psychologist, PT, adolescent, and parent. Graded exposure begins in session 6. The psychologist and PT co-lead a portion of the exposure sessions. During the remaining exposure sessions, the PT leads the exposures while the pain psychologist meets individually with the parent. The final two sessions focus on relapse prevention and future goal setting. **Typical Pain Management.** After randomization, participants allocated to the TPM group will initiate treatment, as indicated by the TPM treatment manual. To ensure dose equivalency, we increased this to 6-Psychology/6-PT with 3 parent-only sessions. In pain management psychology⁵⁰ child and parent sessions focus on biopsychosocial model education, goal setting, pain coping skills training, and cognitive restructuring. PT sessions are based on Guide to Physical Therapy Practice 3.0⁵¹ consisting of 1) therapeutic exercise, 2) balance and proprioception, 3) strength training, and 4) use of modalities (e.g., heat/cold pack).

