6.2.1 Screening Evaluation

Screening

Clinicians will complete the “Clinician Referral: Eligibility Checklist” (Supplemental Materials I – CRF Templates) to indicate if a patient may be eligible for the GET Living study. Once potential participants are identified for participation at SCH, a brief screening phone call will be made by a study staff member to confirm general eligibility requirements (see Supplemental Material II for Phone Screening Form). At this point, the research team will conduct a secondary screening assessment to determine if the patient’s scores on the FOPQ and FDI meet cut-offs for the clinical trial.

Screen Failures

Participants will be considered a screen failure if they do not meet all of the inclusion criteria listed in section 4.1 or if they meet any of the exclusion criteria listed in section 4.2.

Consenting Procedure

Before obtaining formal written assent/consent from patients and their parents, clinical providers at the PPMC and Kaiser will obtain verbal consent to be approached by members of the research team.

Study staff, which will include a research coordinator (RC) or postdoctoral fellow trained by [name], will conduct the consent and assent procedure. Eligible participants will be educated about study procedures or any changes in those procedures. Signed consent/assent forms will be kept in a locked filing cabinet in [name] office.

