6.2.2 Enrollment, Baseline, and Randomization

Enrollment

Study consenting/assenting and enrollment will take place at the initial study visit. All procedures will be completed by a research coordinator (RC) and/or postdoctoral fellows.

Consenting Procedure for Enrollment

This study will follow the *Informed Consent Process for Research* according to the Stanford University Research Compliance Office. Each participant’s consenting process will be recorded by the study RC in the “Screening and Enrollment Log” (MOOP Supplemental Materials I) within an online REDCap CRF. The signed consent/assent documents will be stored in a locked cabinet in the PI, [name], office.

The informed consent process will take place in a private office, and participants will have the opportunity to choose their seating, read the consent form, and ask any questions they may have

at the beginning of the data collection session. Signed consent/assent forms will be stored in a locked file. Participants will be reminded that their involvement in this study is completely voluntary, and that they can withdraw at any time without any negative repercussions whatsoever (e.g., with regard to clinical care or healthcare access). They will also be explicitly told that they may leave any question blank for questionnaires or unanswered for the clinical interview if they do not feel comfortable answering. See Supplement Material for the consent and assent form.

Non-English Speaking Participants – Individuals who do not speak or understand English will not be recruited to the study. While we recognize the limitations of this approach, practical considerations necessitate the inclusion of only those who are able to speak or understand English.

Enrollment date will be recorded in the “Screening and Enrollment Log” ECRF, which will also include documentation of inclusion/exclusion criteria.

Baseline Assessment (BAS):

During the initial study visit, a baseline biomechanical assessment will be conducted and self-reports questionnaires will be completed by the child and parent.

- Child & Parent Baseline Self-Report Measures:

See Supplemental Materials III for baseline self-report measures

- **Patient Biomechanical Assessment** – Motion analysis will be assessed by [name], PhD, of the Motion and sports Performance Laboratory of Stanford Children’s Health. Gait (stride length and velocity)³⁷, drop jump landing³⁷, and dynamic postural control⁴¹ tasks will be performed by the patient.

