For adolescent disability, our estimated treatment effect at 3 and 6-months is 7 with a standard deviation for change of 11.2, yielding power based on the t-test of 65% assuming 58 at end of study. We also created 5000 simulated datasets using a mixed effects model with standard deviations of 11.2 for change and 12.6 at each time point and estimated power by the fraction of simulated datasets in which the treatment difference at 3 and 6-months was significant at level 0.05. This provided a slightly higher power estimate of 67% and an estimated power of 79% if the treatment difference is 8 (1 point larger than expected).

Treatment Assignment Procedures

After a 2-week pre-treatment baseline period, patients will be randomized to either GET Living or TPM and stratified on fear and disability scores (see **Table 6** for scoring criteria). A block

randomization strategy will be used with randomly generated blocks of 2 and 4 to assure near equal distributions across arms and minimize the probability of predicting the next assignment. A randomization spreadsheet with four strata will be created by the study biostatistician, [name] (please see **Table 5** in section 6.2.2 for fear and disability stratification).

Patients will be randomized by an un-blinded research coordinator or postdoctoral fellow. Those who are randomized to the TPM group can opt to participate in GET Living after their study assessments are complete (6.5 months after baseline). They will no longer be considered a participant of this study at that time.

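### The Research Coordinator keeps the complete randomisation lists, and the same role may consent, enrol and randomise; the protocol neither separates these tasks nor describes single release of assignments

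*Combined protocol and SAP*

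**What the plan says.** **Custody (section 3, Study Entry and Randomization).** The four stratum lists are made "prior to the start of patient recruitment with each list long enough to include the total planned study size". On who holds them: "Copies of the randomization lists will be kept by the biostatistician and Research Coordinator and not shared with other members of the team".

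**Consent (section 6.2.1).** This is done by "Study staff, which will include a research coordinator (RC) or postdoctoral fellow".

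**Enrolment (section 6.2.2).** "All procedures will be completed by a research coordinator (RC) and/or postdoctoral fellows". The same section says that each participant's "consenting process will be recorded by the study RC in the" screening and enrolment log.

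**Randomisation (section 9.2, Treatment Assignment Procedures).** "Patients will be randomized by an un-blinded research coordinator or postdoctoral fellow". Sections 6.2.2 and 9.2 describe the sequence only as a spreadsheet with four strata.

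**Stated safeguards (section 3).** There are three: the limit on who holds the lists; random block sizes of two and four, aimed at "minimizing the probability of a blinded staff member predicting the next assignment"; and the timing rule that "Notification of treatment arm allocation will occur at the end of the pre-treatment baseline period".

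**The concern.** Allocation concealment requires that whoever influences entry cannot see the next assignment. Here the role that holds the lists is also one of the two roles allowed to take consent, enrol and randomise. Someone in that position could, even unintentionally, encourage, discourage or time an entry according to the upcoming arm.

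Stratification and adjustment limit selection that acts through baseline FOPQ-C and FDI. Selection on unmeasured prognosis, such as motivation, cannot be removed in analysis. Concealment remains achievable even though section 6.2.3 rules out blinding patients, parents and treating clinicians.

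There is also a procedural gap. A fellow may randomise, yet the lists are not to go beyond the biostatistician and the coordinator, and the protocol does not say how the fellow obtains the assignment.

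**Working it through.** **1. The passages side by side.**

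| Task | Who may do it | Section |
|---|---|---|
| Hold the full lists | Biostatistician, Research Coordinator | 3 |
| Consent and assent | Research coordinator or fellow | 6.2.1 |
| Enrol | Research coordinator and/or fellows | 6.2.2 |
| Randomise | Un-blinded research coordinator or fellow | 9.2 |

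The coordinator role appears in every row. No section requires different people, and none mentions envelopes, a central service or release of one assignment at a time.

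**2. Do the stated safeguards cover a list-holder?** Random block sizes hinder guessing from past allocations, but a list-holder does not need to guess. Delayed notification controls when the arm is announced, not what the holder can see. Restricting the lists to two holders helps only if neither of them enrols.

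**3. How much does the list reveal?** The documents give no figure to reproduce, so this is a simulation.

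- From the protocol: 74 patients; four strata; blocks of two (weight 2/3) or four (weight 1/3); assignment at the end of a baseline averaging two weeks.
- Assumed: uniform accrual over 12 to 48 months; baseline uniform on 7 to 21 days; strata of 19/19/18/18 or 40/20/10/4; stratum already known at consent.
- List: share of patients for whom the next unused slot at consent shows the arm later received.
- No list: share guessed correctly by someone who knows all earlier allocations in the stratum and picks the arm that is behind (coin toss if tied).

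| Accrual (months) | List, equal strata | No list, equal strata | List, 40/20/10/4 | No list, 40/20/10/4 |
|---|---|---|---|---|
| 12 | 0.689 | 0.626 | 0.636 | 0.603 |
| 24 | 0.810 | 0.665 | 0.750 | 0.649 |
| 36 | 0.866 | 0.683 | 0.812 | 0.671 |
| 48 | 0.895 | 0.691 | 0.851 | 0.682 |

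A holder who also counts patients already in baseline does better: 0.867 to 0.962 with equal strata, 0.816 to 0.944 with unequal strata.

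**4. At the moment of assignment.** The list-holder is certain. Without the list but with full history:

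- Block of two: (0.5 + 1)/2 = 0.750.
- Block of four: (0.5 + 2/3 + 2/3 + 1)/4 = 0.708.
- Stated mix: (2/3 × 1.5 + 1/3 × 2.833)/(2/3 × 2 + 1/3 × 4) = 1.944/2.667 = 0.729, or about 0.72 with 74 patients in four finite strata.

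**5. Illustrative bias, net of the no-list guesser.** Suppose every entry is steered, so that patients with prognosis +d are brought in when one arm is expected and −d when the other is. With hit rate g, the arm means shift by +d(2g − 1) and −d(2g − 1), so bias = 2d(2g − 1). The part due to the list is 4d(g_list − g_no list). With d assumed to be 1 to 4 FOPQ-C points, equal strata and the next-slot rule:

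- 12 months: 4 × 1 × (0.689 − 0.626) = 0.25; with d = 4, 1.01.
- 48 months: 4 × 1 × (0.895 − 0.691) = 0.82; with d = 4, 3.26.

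The planned difference in section 9.2 is 22.4 − 5 = 17.4.

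**The case against.** **The overlap is permitted, not shown.** Section 3 speaks of a blinded staff member and section 9.2 of an un-blinded coordinator, which hints at a split among staff. There may be several coordinators. The manual of procedures, cited but not supplied, may separate the roles. All of this stands. A reader might infer that concealment has failed or that one person does everything; the documents do not support that. They do not exclude it either, and no section gives consent or enrolment to the blinded staff. The coordinator's logging of each consent is record-keeping and does not prove involvement in the decision to enrol.

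**A fellow who randomises need not breach the custody rule.** Passing on one assignment is not sharing a list. Agreed: this is an unstated route, not a contradiction.

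**The hit rates are favourable to the concern.** They assume that the stratum is known at consent, but the protocol does not say whether screening or baseline scores define it, and the baseline questionnaires follow consent. If the stratum is unknown, the rate falls to about 53% to 66%. If it is guessed wrongly a quarter of the time (assumed), it is about 60% to 80%. A look 14 days before consent (assumed) gives about 55% to 80% by the next-slot rule, which at 12 months is no better than guessing without the list. The screening call comes before the FOPQ and FDI screening, so no stratum list can be chosen then. These points stand and reduce the size.

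**Larger bias figures are tempting.** Without subtracting the comparator, the same formula gives up to about 6.4 points and a false-positive rate of about 21%. Those figures need 48 months, equal strata, the largest assumed shift and action on every patient. They also charge to the list what guessing from history would already produce: about 3.1 points and 8.6% in that scenario.

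**Conclusion.** The concern holds as a gap in the written plan. Followed as worded, the custody rule allows someone who can see upcoming assignments to consent, enrol and randomise, and no stated safeguard prevents it. Confidence is high for this reading of the text and low for any particular magnitude.

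At consent, the list raises the hit rate from about 60% to 69% to about 64% to 90%, under the assumed accrual, baseline length, stratum sizes and known stratum. If every entry were acted on, the list would add about 0.3 to 1.0 FOPQ-C points of bias at 12 months' accrual and 0.8 to 3.3 at 48 months. These figures show scale and do not predict bias. No power or sample-size figure changes.

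A reader might also infer that the trial has no blinded outcome at all. It does: section 6.2.3 blinds the motion-analysis assessor, although biomechanics is exploratory. In any case, blinded assessment would not reveal selection at entry, so the argument does not rest on it.

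**What to change.** In section 3, replace the custody sentence so that:

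- only the biostatistician, or a central or electronic system, holds the lists, and nobody who screens, consents, enrols or books patients can view them;
- each assignment is released singly, after baseline is complete and the stratum is recorded;
- the role that receives the assignment is named, including when a fellow randomises;
- any unused list portions that an enrolling coordinator has seen are regenerated.

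If the manual of procedures already separates the roles, stating that rule in the protocol is enough.

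The cost is a few sentences, one message or system step per patient, and a back-up for when the releaser is unavailable. The fix does not remove all predictability: staff who know past allocations could still guess about 72% at the moment of assignment.

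Raise separately: section 4.1 admits patients below FOPQ 35 or FDI 13 on clinician referral, section 3 gives no such route, and Table 5 has no stratum for them. These passages must be reconciled.
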